3.7.1.5 Early Termination/End of Treatment (+ 7 days)

At the early termination/end of treatment (EoTx) visit the following will be assessed:

1. Review dietary recommendations and compliance.
2. CCI [REDACTED]

Protocol 156-13-211

3. Record vital signs (post-void weight, seated heart rate, and calibrated blood pressure measurement).
4. Collect blood for serum chemistry, serum creatinine, ALT, serum sodium and hematology and coagulation.
5. CCI [REDACTED]
6. CCI [REDACTED]
7. Collect urine for urinalysis, urine osmolality (optional), urine specific gravity.
8. Perform urine pregnancy test on WOCBP. If positive, a follow-up serum test will be performed.
9. An optional directed physical examination may be performed to focus on PKD-related signs and symptoms.
10. Assess tolerability/dosing review of IMP.
11. Enter subject status in IRT, including any dose-regimen changes since the previous entry.
12. Collect and reconcile returned IMP; assess compliance.
13. Update concomitant medications.
14. Assess AEs.

3.7.1.6 7-day Follow-up Visit (+ 7 days)

1. Record vital signs (post-void weight, seated heart rate, and calibrated blood pressure measurement).
2. Collect blood for serum creatinine and ALT.
3. CCI [REDACTED]
4. Perform urine pregnancy test on WOCBP. If positive, a follow-up serum test will be performed.
5. Enter subject status in IRT.
6. Update concomitant medications.
7. Assess AEs.

Protocol 156-13-211

3.7.2 Safety Assessments

3.7.2.1 Adverse Events

Refer to [Section 5, Reporting of Adverse Events](#).

3.7.2.2 Clinical Laboratory Assessments

Central laboratory non-fasting serum laboratory tests will be performed. It is preferable to collect the clinical laboratory samples from each subject at a consistent time of day throughout the trial, and to recommend that the subject have a similar diet, avoiding variation in protein intake (especially cooked meat protein) and exercise pattern in order to reduce variability in the samples over time.

CCI
 [REDACTED]
 [REDACTED]
 [REDACTED]
 [REDACTED]
 [REDACTED]
 [REDACTED]
 [REDACTED]
 [REDACTED]
 [REDACTED]

A list of the specific clinical laboratory assessments is presented in [Table 3.7.2.2-1](#).

Clinical laboratory samples will be collected and sent to the central laboratory at the following time points:

Screening: Hematology and coagulation panel, serum chemistry panel, liver function panel (AST, ALT, alkaline phosphatase, bilirubin direct [BT]) serum sodium, serum creatinine, urinalysis panel, urine osmolality (optional), urine specific gravity, urine pregnancy test (WOCBP) and hepatitis (optional).

Monthly visits (± 7 days): ALT (for the first 18 months for subjects enrolled from other tolvaptan ADPKD trials and Trial 156-13-210 while trial remains blinded), serum sodium, and serum creatinine (all subjects), urinalysis, urine osmolality (optional), urine specific gravity, and urine pregnancy test (every 3 months in WOCBP). CCI
 [REDACTED]

Every 3 months: (± 14 days): ALT (after 18 months of treatment for subjects enrolled from other ADPKD tolvaptan trials, or from Trial 156-13-210 after the trial is unblinded, and for subjects enrolled from Trial 156-08-271), serum sodium and serum creatinine,

Protocol 156-13-211

urinalysis panel, urine pregnancy test (WOCBP), urine osmolality (optional), and urine specific gravity. P^{CCI} [REDACTED]

Early Termination/EoTx (+ 7 days): Serum chemistry panel, hematology and coagulation panel, ALT, serum sodium and serum creatinine, ^{CCI} [REDACTED], urinalysis panel, urine pregnancy test (WOCBP), urine osmolality (optional), and urine specific gravity.

7-day Follow-up visit (+ 7 days): ALT, serum creatinine, and urine pregnancy test (WOCBP).

Table 3.7.2.2-1 Clinical Laboratory Assessments	

Hematology and Coagulation Panel: Hemoglobin Platelet count Mean corpuscular hemoglobin concentration (MCHC) Mean corpuscular volume (MCV) Red blood cell (RBC) count White blood cell (WBC) count with differential Prothrombin time (PT) as international normalized ratio (INR) Activated partial thromboplastin time (aPTT)
 
Urinalysis Panel: Appearance Color Blood Glucose Microscopic analysis, WBC/RBC counts per high power field pH Protein
 
Urine Chemistry Osmolality (optional) Specific gravity
 
Additional Tests: Urine (or serum) pregnancy for WOCBP Hepatitis (optional)
	
Serum Chemistry Panel: Albumin Blood urea nitrogen (BUN) Serum calcium Carbon dioxide Serum chloride Gamma-glutamyl transpeptidase Cholesterol, total Glucose Lactate dehydrogenase (LDH) Phosphorus Potassium Protein, total Uric acid
 
Liver Function Panel: Alkaline phosphatase (ALP) Alanine aminotransferase (ALT) Aspartate aminotransferase (AST) Bilirubin, total (BT) Bilirubin, direct

Creatinine	Sodium

If liver function panel, sodium and/or serum chemistry assessments are scheduled at the same visit, all values should be determined from the same blood sample. Blood testing for hepatitis will be optional for all subjects. Urine pregnancy testing will be performed

Protocol 156-13-211

with commercially available, high-sensitivity kits supplied to the subject by the site (acquired by the sponsor).

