3.7.1.3 Monthly Visit (± 7 days)

The following subjects will return for a monthly visit to assess safety and tolerability of IMP and to monitor liver function.

- Subjects enrolling from the double-blind Trial 156-13-210 will have monthly trial visits/ALT level assessments for the first 18 months while treatment code from Trial 156-13-210 remains blinded, to ensure that they have adequate safety monitoring during this period of susceptibility. Once unblinding occurs, it can be determined which subjects received tolvaptan in Trial 156-13-210. These subjects may have their trial visits/hepatic transaminase monitoring change to every 3 months sooner as their previous tolvaptan exposure in Trial 156-13-210

Protocol 156-13-211

can count towards the 18-month threshold. The investigator will need to discuss the change in frequency with the medical monitor before instituting the change.

- Subjects from prior tolvaptan trials other than Trial 156-08-271 will have monthly trial visits/ALT level assessments for the first 18 months. After that, the trial visits/ALT monitoring will be conducted every 3 months after the change in frequency is confirmed with the medical monitor.
- Subjects enrolling from the open-label Trial 156-08-271 who have greater than 18 months of exposure to tolvaptan will have trial visits/ALT monitoring conducted every 3 months.

The following will be assessments will be completed:

1. Review dietary recommendations and compliance.

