3.7.2 Safety Assessments

3.7.2.1 Adverse Events

Refer to [Section 5, Reporting of Adverse Events](#).

Protocol 156-13-211

CCI [REDACTED]

CCI [REDACTED]

A list of the specific clinical laboratory assessments is presented in [Table 3.7.2.2-1](#).

Clinical laboratory samples will be collected and sent to the central laboratory at the following time points:

Screening: Hematology and coagulation panel, serum chemistry panel, liver function panel (AST, ALT, alkaline phosphatase, bilirubin direct [BT]) serum sodium, serum creatinine, urinalysis panel, urine osmolality (optional), urine specific gravity, urine pregnancy test (WOCBP) and hepatitis (optional).

Monthly visits (± 7 days): ALT (for the first 18 months for subjects enrolled from other tolvaptan ADPKD trials and Trial 156-13-210 while trial remains blinded), serum sodium, and serum creatinine (all subjects), urinalysis, urine osmolality (optional), urine specific gravity, and urine pregnancy test (every 3 months in WOCBP). CCI [REDACTED]

Every 3 months: (± 14 days): ALT (after 18 months of treatment for subjects enrolled from other ADPKD tolvaptan trials, or from Trial 156-13-210 after the trial is unblinded, and for subjects enrolled from Trial 156-08-271), serum sodium and serum creatinine, urinalysis panel, urine pregnancy test (WOCBP), urine osmolality (optional), and urine specific gravity. CCI [REDACTED]

Early Termination/EoTx (+ 7 days): Serum chemistry panel, hematology and coagulation panel, ALT, serum sodium and serum creatinine, CCI [REDACTED] urinalysis

Protocol 156-13-211

panel, urine pregnancy test (WOCBP), urine osmolality (optional), and urine specific gravity.

7-day Follow-up visit (+ 7 days): ALT, serum creatinine, and urine pregnancy test (WOCBP).

Table 3.7.2.2-1 Clinical Laboratory Assessments	

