3.4 Trial Visit Window

Due to the extended duration of the study, the individual patient data will be summarized by period.

For assessments recorded at clinic visits, except for the hepatic monitoring for the subjects from Trial 156-08-271, data will be derived by mapping the study day of the assessment into corresponding time windows as specified in [Table 3.4.1](#). Study day is calculated as: date of assessment - date of enrollment (ie, screening or baseline date) + 1. If there are multiple observations within the same study time window, only the last observation within that study week will be used for the summary tables. The time window mapping rules are applicable to all post first dose safety and efficacy assessments (unless otherwise stated) that are assessed at the scheduled or unscheduled visits (excluding early termination visits/end of treatment visits).

Table 3.4.1 Mapping of clinic visit assessments to study month (except for hepatic monitoring for Subjects from Trial 156-08-271)

Study Month	Study Day Interval
Monthly Visit	
Month 1	2 – 46
Month 2	47 – 76
Month 3	77 – 107
Month 4	108 – 137
Month 5	138 – 168
Month 6	169 – 198
Month 7	199 – 229
Month 8	230 – 259
Month 9	260 – 290
Month 10	291 – 320
Month 11	321 – 351
Month 11	352 – 381
Month 13	382 – 412
Month 14	413 – 442

Protocol 156-13-211

Month 15	443 – 473
Month 16	474 – 503
Month 17	504 – 534
Month 18	535 – 595
Every 3 Months	
Month 21	596 – 686
Month 24	687 – 778
Month 27	779 – 869
Month 30	870 – 961
Month 33	962 – 1052
Month 36	1053 – 1144
Month 39	1145 – 1235
Month 42	1236 – 1327
Month 45	1328 – 1418
Month 48	1419 – 1510
Month 51	1511 – 1601
...	...

Note: Early Termination/End of Treatment (\pm 7 days)

Once Trial 156-13-210 unblinding occurs, it can be determined which subjects received tolvaptan in Trial 156-13-210. These subjects may have their trial visits/hepatic transaminase monitoring changed to every 3 months sooner as their previous tolvaptan exposure in Trial 156-13-210 can count towards the 18-month threshold.

For assessments for hepatic monitoring recorded at clinic visits, for the subjects from Trial 156-08-271, data will be derived by mapping the study day of the assessment into corresponding time windows as specified in [Table 3.4.2](#).

Study Month	Study Day Interval
Every 3 Months (\pm 45 days)	
Month 3	2 – 137
Month 6	138 – 229
Month 9	230 – 320
Month 12	321 – 412
Month 15	413 – 503
Month 18	504 – 595
Month 21	596 – 686
Month 24	687 – 778
Month 27	779 – 869

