8.4 Serum Sodium

The following will be summarized by parent study (and prior treatment):

- Serum sodium excursions above 145, 150, or 155 mmol/L or below 136, 130, or 125 mmol/L

Interruptions of protocol-specified therapies for hypernatremia or hyponatremia.

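### SAP 8.4 tabulates sodium excursions by parent study without allowing for monthly versus 3-monthly sampling, so for equal follow-up the 156-08-271 column flags fewer subjects at the same true risk

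*Protocol*

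**What the plan says.** **Analysis.** Sodium excursions beyond fixed high and low thresholds are a listed safety endpoint (Protocol 3.5.1). SAP 8.4 introduces them with "The following will be summarized by parent study (and prior treatment". SAP 8 adds that safety summaries are descriptive, use all available data and involve no inferential analysis. The readable text of SAP 8.4 names no denominator per sample or per unit of exposure, and no common sampling schedule.

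**Who is sampled when.** Footnote b of Protocol Table 3.7-1 assigns monthly visits below 18 months on tolvaptan and 3-monthly visits above. Section 3.7.1.3 opens with "The following subjects will return for a monthly visit to assess safety and tolerability of IMP" and then lists them; Trial 156-08-271 entrants "who have greater than 18 months of exposure to tolvaptan will have trial visits/ALT monitoring conducted every 3 months". Sodium and creatinine are drawn at both kinds of visit (3.7.1.3 and 3.7.1.4).

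**Wording of 3.7.2.2.** Under the monthly heading, ALT carries a cohort limit, "ALT (for the first 18 months for subjects enrolled from other tolvaptan ADPKD trials and Trial 156-13-210 while trial remains blinded", while the other two tests are given as "serum sodium, and serum creatinine (all subjects". The UK version has the same tag: "and serum creatinine (all subjects), urinalysis, urine osmolality (optional), urine". The 3-monthly entry in the same section lists both tests again: "for subjects enrolled from Trial 156-08-271), serum sodium and serum creatinine".

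**SAP windows.** SAP 3.4 maps clinic assessments to the monthly windows of Table 3.4.1, "except for the hepatic monitoring for the subjects from Trial 156-08-271". Sodium and creatinine from those subjects therefore fall under the monthly windows through Month 18.

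**The concern.** The chance that a subject is ever seen with an abnormal sodium value rises with the number of times sodium is measured. The exposure-based visit schedule makes that number differ systematically by parent study. A reader of the SAP 8.4 table will naturally set the long-exposed 156-08-271 column beside the 156-13-210 prior-placebo column. Part of any difference will come from the sampling, and it will make long exposure look safer. The trial's sole stated objective is long-term safety and its output is descriptive tables, so the reading of such a table matters even though no test is planned.

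**Working it through.** The plan gives no figure to reproduce. The inputs are the visit frequencies and an assumed probability.

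**Step 1: scheduled samples over the first 18 months in this trial, for equal follow-up.**

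- 156-13-210 prior-placebo subjects, below 18 months of tolvaptan throughout: 18 / 1 = 18.
- 156-08-271 subjects, already beyond 18 months of exposure: 18 / 3 = 6.
- Ratio: 18 / 6 = 3.0. Per year it is 12 / 4 = 3.0.

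Prior-tolvaptan subjects from 156-13-210 may move to 3-monthly visits early once that trial is unblinded, so they lie between the two. If a full 12 months of earlier exposure counted (an assumption), they would have 18 − 12 = 6 monthly samples and then 12 / 3 = 4, giving 10. Once every cohort is past its 18-month threshold, the frequencies are the same.

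**Step 2: probability of at least one flagged sample.** Let p be the excursion probability per sample, equal in all cohorts, with independent samples. The share ever flagged in k samples is 1 − (1 − p)^k. For p = 1%:

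- k = 18: 1 − 0.99^18 = 16.5%.
- k = 6: 1 − 0.99^6 = 5.9%.

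| Assumed p | 18 samples | 6 samples | Ratio |
|---|---|---|---|
| 0.1% | 1.8% | 0.6% | 2.98 |
| 0.5% | 8.6% | 3.0% | 2.91 |
| 1% | 16.5% | 5.9% | 2.83 |
| 2% | 30.5% | 11.4% | 2.67 |
| 5% | 60.3% | 26.5% | 2.28 |

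**Step 3: effect of correlation.** Repeated sodium values in one person are not independent. In the extreme where a subject is flagged either at every sample or at none, the ratio is 1. The true ratio therefore lies between 1 and roughly the figures shown.

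**Step 4: do the SAP windows remove the imbalance?** No. SAP 3.4 keeps the last value in each window. Through Month 18 a monthly attender can fill 18 windows of Table 3.4.1. A 156-08-271 subject on 3-monthly visits fills 6 and leaves 18 − 6 = 12 empty. SAP 5.2 summarizes observed values only, so the empty windows add nothing.

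**Step 5: effect of the fix.** Counting only Months 3, 6, 9, 12, 15 and 18 gives k = 6 in every cohort. At p = 1% each column then shows 5.9%.

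**The case against.** The strongest objection is that the unequal sampling is a deliberate feature of the visit design, that the plan is descriptive, and that a careful reader can allow for it. The first two parts are true: no error rate or power is affected. The third is not available to the reader as planned, because the readable text does not ask for samples or exposure time beside the counts.

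The size is also open to challenge. No per-sample probability appears in the documents, independence is unrealistic, and 18 against 6 assumes equal follow-up. Under the global protocol, subjects from trials other than 156-13-210 leave when tolvaptan becomes available. These objections limit the magnitude; they do not remove the imbalance in scheduled samples. In addition, Protocol 7.5.2.4 (Serum Sodium) is in the table of contents but its text cannot be read in the public copy, so whether it deals with sampling frequency cannot be checked.

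A reader might infer more: that 3.7.2.2 orders monthly sodium and creatinine for every subject throughout, so that a site could test the same long-exposure subject monthly or 3-monthly. The documents do not support this. The all-subjects tag sits under the monthly-visit heading, attendance at those visits is restricted by footnote b and 3.7.1.3, and the 3-monthly entry of the same section would be redundant if everyone were drawn monthly. A reader might also infer that the SAP adopts monthly sampling for 156-08-271 subjects. Table 3.4.1 only assigns data to windows; it schedules no draws. A visit at about Day 91 ± 14 (77 to 105) falls inside the Month 3 window (77 to 107).

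**Conclusion.** The point holds as an ascertainment imbalance in a planned safety table. For equal follow-up over 18 months, the schedule gives 156-08-271 entrants about one third of the sodium samples of 156-13-210 prior-placebo subjects, and nothing visible in SAP 8.4 allows for it. Under independence and equal true risk, the share ever flagged differs by a factor of about 2.3 to 3.0 for p between 0.1% and 5%; correlation moves that towards 1. The direction is predictable and the size is not known from the documents. It is a worthwhile, inexpensive improvement.

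The wording of 3.7.2.2 is secondary and minor. The contrast between the restricted ALT tag and the all-subjects tag is ambiguous against the attendance rules, and SAP 3.4 excepts only hepatic data of 156-08-271 subjects although their whole visit is 3-monthly. Rewording those passages alone would not correct the sodium table.

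**What to change.** 1. In SAP 8.4, add excursion incidence by parent study and prior treatment on the 3-monthly scheduled samples common to all cohorts: nominal Months 3, 6, 9 and so on, one value per visit, with unscheduled samples left out.
2. Keep the all-samples count beside it, and give the number of sodium samples, or the exposure time, per subject in each column.
3. Reconcile the all-subjects tag in the monthly entry of Protocol 3.7.2.2 (global and UK) with Table 3.7-1 footnote b and 3.7.1.3, and align the SAP 3.4 windows for non-hepatic data of 156-08-271 subjects with the result. The sponsor decides the frequency.

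The cost is one extra table from data already collected, plus a short clarification. The common-schedule count ignores some monthly samples and may miss brief excursions between 3-monthly visits; those samples remain in the all-samples count.

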3.7.2.3 Physical Examination and Vital Signs

A full physical examination will be performed and documented at the screening visit although this may be combined with the last visit from the previous trial. At other visits, an optional directed physical examination may be performed to focus on ADPKD-related signs and symptoms. In some geographic regions, more frequent subject visits may be the norm; however vital signs and clinically significant physical findings will be recorded as an unscheduled visit in the electronic case report form (eCRF) as applicable. Any changes in medication or AEs will be recorded in the eCRF.

Height will be measured only at screening. Body weight will be taken post-void. It is preferable to use the same scale for each measurement. Clinic scales should be calibrated at least yearly. The investigator or his/her appointed designee is primarily responsible to perform the physical examination. If the appointed designee is to perform the physical examination, he/she must be permitted to do so by local regulations and his/her name must be included on any globally and locally required documents (eg, individual must be added for all sites on a US Food and Drug Administration (FDA) Form 1572, where local regulations allow, while local regulations determine their being named in the ICF). Whenever possible, the same individual should perform all physical examinations. Any undesirable condition present at a post-treatment physical examination that was not present at the baseline examination should be documented as an AE and followed to a satisfactory conclusion.

Vital sign data, including seated blood pressure, heart rate, height, and weight will be taken at the visits identified in the Schedule of Assessments ([Table 3.7-1](#)).

3.7.2.4 Assessment of Liver Symptoms, Signs or Test Abnormalities

Testing for hepatic transaminase (ALT/AST), alkaline phosphatase, bilirubin direct, and BT will be performed during screening. Subjects enrolling from the double-blind Trial 156-13-210 will have monthly ALT assessments for the first 18 months while the treatment code from Trial 156-13-210 remains blinded to ensure that all subjects have adequate safety monitoring during this period of susceptibility. Once unblinding occurs, it can be determined which subjects received tolvaptan in Trial 156-13-210. These subjects may have their trial visits/hepatic transaminase monitoring changed to every 3 months sooner as their previous tolvaptan exposure in Trial 156-13-210 can count towards the 18-month threshold.

Protocol 156-13-211

Following the first 18 months, ALT assessments will be made every 3 months for Trial 156-13-210 subjects and for subjects from other tolvaptan ADPKD trials besides Trial 156-08-271.

Subjects enrolling from the open-label Trial 156-08-271 who have tolvaptan exposure greater than 18 months will continue with ALT monitoring every 3 months.

Subjects enrolling from prior tolvaptan trials besides Trial 156-08-271 will have monthly ALT assessments for the first 18 months. Upon reaching 18 months of exposure and after confirmation from the medical monitor, the frequency of ALT monitoring for these subjects will occur every 3 months.

ALT will also be assessed at the Early Termination/EoTx visit and at the 7-day Follow-up visit.

Management of liver abnormalities is discussed in the paragraphs below.

3.7.2.4.1 Liver Test Abnormalities and Interruption/Discontinuation of Investigational Medicinal Product

An ALT elevation $2 \times$ ULN or the appearance of any suspicious symptom or sign should trigger prompt testing of hepatic function (ie, within 72 hours). Local laboratory testing is acceptable, ideally with a concurrent central laboratory sample for confirmation.

Any transaminase or bilirubin values which exceed $2 \times$ ULN should also prompt immediate retesting within 72 hours. While values remain in an abnormal range, testing frequency should be increased to at least weekly for the first month, gradually returning to monthly, or every three months as indicated by the results.

Liver transaminase or bilirubin levels reaching or exceeding $2 \times$ ULN that have an uncertain or rapidly increasing trajectory should prompt at least temporary IMP interruption. Tolvaptan should not be resumed until monitoring indicates abnormalities have resolved, are stable, or are not rapidly increasing, and then only with an increased frequency of monitoring.

Subjects would not typically be allowed to resume treatment with tolvaptan if they have:

- transaminase levels rise above $8 \times$ ULN,
- transaminase levels are $> 5 \times$ ULN for more than 2 weeks, or
- concurrent elevations of transaminase $> 3 \times$ ULN and BT $> 2 \times$ ULN.

Subjects with these levels of abnormality may be re-challenged with IMP if abnormalities were adjudicated as having a $< 50\%$ likelihood of being related to IMP (per DILI network

Protocol 156-13-211

[DILIN] probability criteria)¹⁰ by an independent hepatic adjudication committee (HAC) and the investigator and medical monitor agree to an intensive monitoring plan to mitigate risk. The subject must also be willing to comply with these monitoring measures, be informed of the potential risks, and consent to IMP re-challenge.

3.7.2.4.2 Requirements for Special Reporting Using the Liver Disease Electronic Case Report Form and Immediately Reportable Event Form

The purpose of the liver disease eCRF and optional additional testing is to facilitate review of each subject who presents with, or develops a liver abnormality during the trial and to determine the probable cause(s) of these abnormalities. The review will be performed by a blinded, independent, HAC using DILIN probability criteria (< 25% = unlikely, 25% to 50% = possibly, 51% to 75% = probably, 76% to 95% = very likely, > 95% = definite).¹⁰ The result of these analyses may be presented separately from the CSR.

The investigator must complete a special liver disease eCRF for any subject who:

1. Discontinues treatment due to a liver-related AE,
2. Reports a serious liver-related AE,
3. Has normal screening levels and develops ALT or AST levels $\geq 3x$ ULN,
4. Has normal screening levels and develops BT levels $\geq 2x$ ULN, or
5. Has an abnormal screening level and develops abnormalities in that test that are > 2x the upper limit of their highest screening value.

CCI [REDACTED]
[REDACTED]
[REDACTED] Additional clinical testing (such as testing for hepatitis serology) may also be indicated and their results reported according to local guidelines. The liver eCRF and Immediately Reportable Event (IRE) form (see [Section 5.3](#)) should be updated as new information becomes available.

CCI [REDACTED]
[REDACTED]
[REDACTED]
[REDACTED]
[REDACTED]
[REDACTED]

Protocol 156-13-211

CCI

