3.4.3 Exclusion Criteria

Subjects will be excluded if they meet any of the exclusion criteria in [Table 3.4.3-1](#).

1.	WOCBP who do not agree to practice 2 different methods of birth control or remain abstinent during the trial and for 30 days after the last dose of IMP. If employing birth control, 2 of the following precautions must be used: vasectomy of partner, tubal ligation, vaginal diaphragm, intrauterine device, birth control pill, birth control implant, birth control depot injection, condom, or sponge with spermicide.
2.	Women who are breast-feeding and/or who have a positive pregnancy test result prior to receiving IMP.
3.	Need for chronic diuretic use.
4.	Hepatic impairment based on liver function abnormalities other than that expected for ADPKD with cystic liver disease during screening based on recent historical laboratory values (in the last 3 months).
5.	Subjects with contraindications to required trial assessments (contraindications to optional assessments, eg, MRI are not a limitation).
6.	Subjects who, in the opinion of the investigator or medical monitor, have a medical history or medical finding inconsistent with safety or trial compliance. This includes prior evidence of significant hepatic injury deemed to be related to tolvaptan use.

WOCBP=women of childbearing potential; IMP=investigational medicinal product

Non-childbearing potential in women is defined as female subjects who are surgically sterile (ie, have undergone bilateral oophorectomy or hysterectomy) or female subjects who have been postmenopausal for at least 12 consecutive months.

Subjects may be rescreened, at the discretion of the medical monitor, if the exclusion characteristic has changed or resolved. In the event that a subject is rescreened, a new ICF must be signed and a new screening number assigned and screening procedures repeated.

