5.3 Immediately Reportable Events

The investigator must immediately report within 24 hours after either the investigator or site personnel become aware of any SAE, new liver laboratory abnormality requiring special liver eCRF completion, or confirmed pregnancy, by telephone or by fax to Quintiles (drug safety service) as outlined in [Appendix 1](#). An IRE form must be completed and sent by fax, email or overnight courier to the sponsor. (Please note that the IRE form is NOT the AE eCRF).

Nonserious events that require discontinuation of IMP (including laboratory abnormalities) should be reported to the sponsor within 3 working days. The IRE form must be completed and sent by fax, email, or overnight courier to the sponsor.

Subjects experiencing SAEs should be followed clinically until their health has returned to baseline status, or until all parameters have returned to normal, or have otherwise been explained. It is expected that the investigator will provide or arrange appropriate supportive care for the subject.

Protocol 156-13-211

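### When a transaminase and bilirubin are both raised at screening, the liver eCRF laboratory triggers can miss a case that meets Hy's laboratory criteria and a no-resume threshold

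*Protocol*

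**What the plan says.** Protocol section 3.7.2.4.2 lists five reasons for completing the special liver disease eCRF, and the UK version has the same list. Two are clinical:

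- Criterion 1: "Discontinues treatment due to a liver-related AE"
- Criterion 2: "Reports a serious liver-related AE"

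Three are laboratory triggers:

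- Criterion 3: "Has normal screening levels and develops ALT or AST levels $\geq 3x$ ULN"
- Criterion 4: "Has normal screening levels and develops BT levels $\geq 2x$ ULN, or"
- Criterion 5: "Has an abnormal screening level and develops abnormalities in that test that are > 2x the upper limit of their highest screening value"

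The section gives the purpose of the form as supporting case review by the blinded hepatic adjudication committee (HAC). Under section 3.7.7, HAC results go to the IDMC at least quarterly.

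Reporting follows the same thresholds. The definition of an immediately reportable event (IRE) in section 5.1 refers to the laboratory thresholds for the hepatic eCRF. The 24-hour rule in section 5.3 covers "any SAE, new liver laboratory abnormality requiring special liver eCRF completion, or confirmed pregnancy".

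Section 3.7.2.4.1 gives three thresholds at which treatment would not typically be resumed: transaminases above 8x ULN, above 5x ULN for more than 2 weeks, or "concurrent elevations of transaminase" above 3x ULN with total bilirubin (BT) above 2x ULN. Hy's laboratory criteria in section 3.5.1 use the same 3x and 2x limits, without alkaline phosphatase (ALP) at or above 2x ULN. None of these is adjusted for the screening value.

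Subjects with abnormal screening tests can enrol. Exclusion 4 bars only "Hepatic impairment based on liver function abnormalities other than that expected for ADPKD with cystic liver disease during screening" and sets no numeric limit.

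**The concern.** The reporting trigger and the outcomes it serves use different scales. Hy's criteria and the no-resume thresholds are anchored to ULN, whereas the trigger for an abnormal screening test is anchored to the subject's own value and rises with it. A subject can therefore reach a hepatic outcome that the protocol itself singles out while the laboratory part of the eCRF list stays silent. The IRE definition and the 24-hour laboratory report inherit that silence.

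Section 2.1 says the trial is meant to define the potential for drug-induced liver injury more precisely, and reports that only 3 tolvaptan subjects had met Hy's laboratory criteria to date. With so few cases, a route by which one could escape routine adjudication is worth closing. Section 3.7.2.4.1 also makes HAC adjudication a precondition of re-challenge after a no-resume threshold, yet reaching that threshold is not itself a reason for the eCRF.

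**Working it through.** The plan gives no figure to reproduce. The check applies criteria 3 to 5 as written and compares them with the fixed thresholds. All values are multiples of ULN. A0 and B0 are the highest screening ALT and BT; A and B are the later values. The odd phrase in criterion 5 about an upper limit is read as the highest screening value itself.

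**When criterion 5 is looser than the fixed limits.** An abnormal test triggers only if A > 2 x A0 or B > 2 x B0.

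- ALT above 3 with no trigger needs 3 < A ≤ 2 x A0, so A0 > 1.5.
- BT above 2 with no trigger needs 2 < B ≤ 2 x B0, so B0 > 1, which is any abnormal screening BT.
- ALT above 5 with no trigger needs A0 > 2.5.
- ALT above 8 with no trigger needs A0 > 4.

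**Hy's cases, read test by test.** Criterion 5 speaks of the particular test that was abnormal, which supports this reading. AST is taken as normal at screening and below 3 later, and ALP as below 2 throughout.

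| Screening ALT, BT | Later ALT, BT | Criterion 5 limits | Outcome |
|---|---|---|---|
| 1.8, 1.2 | 3.5, 2.3 | 3.6, 2.4 | No laboratory trigger |
| 2.0, 1.2 | 3.5, 2.2 | 4.0, 2.4 | No laboratory trigger |
| 1.4, 1.2 | 3.5, 2.2 | 2.8, 2.4 | Criterion 5, through ALT |
| 1.8, normal | 3.5, 2.2 | 3.6, not applicable | Criterion 4, through BT |
| Normal, 1.2 | 3.5, 2.2 | Not applicable, 2.4 | Criterion 3, through ALT |

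In the first row the ratios are 3.5/1.8 = 1.94 and 2.3/1.2 = 1.92, both below 2. The values still exceed 3 and 2, so Hy's laboratory criteria and the concurrent-elevation threshold are both met. A missed Hy's case on this reading needs both a screening transaminase above 1.5 and a screening BT above 1.

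**Alternative reading.** If criteria 3 and 4 require every screening liver test to be normal, one abnormal test is enough. Rows 4 and 5 would then meet no laboratory criterion.

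**Other no-resume thresholds.** These need only ALT to be abnormal at screening. From 2.6, the criterion 5 limit is 5.2. More than 2 weeks at 5.1 (ratio 5.1/2.6 = 1.96) meets the second threshold with no trigger. From 4.2, a later 8.2 (ratio 1.95) exceeds 8 with no trigger, but that starting value is an edge case.

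**Where there is no transaminase gap.** For screening ALT from just above 1 up to 1.5, criterion 5 is no looser than 3x ULN. At 1.1 it fires above 2.2, earlier than for a subject with a normal screening value.

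**The case against.** A reader might infer that the Hy's endpoint itself would be under-counted. The SAP does not support that. Its paragraph on potential Hy's Law cases, just before section 8.3, calls for an incidence table and listing from laboratory values at 3x ULN for ALT or AST and 2x ULN for bilirubin. It has no screening-value condition and no link to the eCRF, so the worked case would be counted.

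A reader might also infer that any single abnormal screening test lets a Hy's case through. On the test-by-test reading it does not.

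The window is narrow. From screening values of 1.8x and 1.2x, ALT must peak above 3.0x and no higher than 3.6x, with BT above 2.0x and no higher than 2.4x. Retesting within 72 hours and then at least weekly would show a further rise crossing criterion 5. AST that was normal at screening and reaches 3x ULN triggers criterion 3. Subjects must also pass exclusions 4 and 6.

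Other routes exist:

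- Not resuming treatment may be recorded as discontinuation for a liver-related AE, which is criterion 1.
- A serious event meets criterion 2 and the 24-hour rule.
- Section 5.3 requires an IRE form within 3 working days for nonserious events, including laboratory abnormalities, that require discontinuation.
- Section 5 names liver abnormalities as AEs of special interest, and section 5.1 makes such AEs IREs.

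These points stand and narrow the gap. They do not close it. Each route depends on the investigator's judgement, since section 5.1 makes a laboratory value an AE only if the investigator considers it an abnormal change for that subject. Nothing in the visible text makes a Hy's case serious automatically, and section 3.7.5 treats interruption separately from permanent discontinuation. The special-interest route is neither among the five eCRF criteria nor named in the 24-hour list.

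It would go too far to say that nothing could start an adjudication before re-challenge, because a proposed re-challenge itself calls for one. Nor do the documents support describing the affected subjects as having the least hepatic reserve.

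**Conclusion.** The gap is real but limited. Subjects with a screening transaminase above 1.5x ULN and BT above 1x ULN can meet Hy's laboratory criteria and the concurrent-elevation threshold without meeting any laboratory trigger for the liver eCRF. Subjects with screening ALT above 2.5x ULN can similarly meet the threshold of more than 5x ULN for over 2 weeks. At stake are the eCRF detail, the 24-hour laboratory report and the causality adjudication that informs the IDMC. The laboratory Hy's count is unaffected.

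This rests on three assumptions: the test-by-test reading, criterion 5 meaning twice the highest screening value, and no further condition in the redacted text that follows the list. The all-tests-normal reading would widen the gap. The documents give no distribution of screening values, so the frequency cannot be estimated. This is a cheap improvement to safety oversight and to ascertainment of adjudicated liver injury; with the frequency unknown and other routes available, a stronger label is not warranted.

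**What to change.** Reconcile the passages by adding one reporting criterion to section 3.7.2.4.2 in both the global and UK versions. Any subject, whatever the screening value, who meets the Hy's laboratory thresholds of section 3.5.1 or any of the three no-resume thresholds already in section 3.7.2.4.1 requires the liver eCRF, an IRE form and HAC review. Keep criterion 5 as an additional trigger, and reword its reference to an upper limit, since a single screening value has none. State whether normal screening levels in criteria 3 and 4 means the test concerned or all liver tests.

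This changes reporting and adjudication only. It reuses limits already in the protocol and alters no dosing, interruption or resumption rule. The cost is one line in each protocol version, an edit check in the data capture system, and a few more eCRFs and adjudications by a committee that already exists.
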